9.2.4 Serious Adverse Events

Serious Adverse Event (SAE): An AE or suspected adverse reaction is considered “serious” if, in the view of either the site principal investigator or sponsor, it results in any of the following outcomes:

- Death,
- A life-threatening AE*,
- Inpatient hospitalization or prolongation of existing hospitalization,

- A persistent or significant incapacity or substantial disruption of the ability to conduct normal life functions, or
- A congenital anomaly/birth defect.
- Important medical events that may not result in death, be life-threatening, or require hospitalizations may be considered serious when, based upon appropriate medical judgment they may jeopardize the patient or subject and may require medical or surgical intervention to prevent one of the outcomes listed in this definition. Examples of such medical events include allergic bronchospasm requiring intensive treatment in an emergency room or at home, blood dyscrasias or convulsions that do not result in inpatient hospitalization, or the development of drug dependency or drug abuse.

* Life-threatening AE. An AE is considered “life-threatening” if, in the view of either the site principal investigator or sponsor, its occurrence places the patient or subject at immediate risk of death. It does not include an AE that, had it occurred in a more severe form, might have caused death.

SAEs will be:

- Assessed for severity and relationship to study product and alternate etiology (if not related to study product) by a licensed study physician listed on the Form FDA 1572 as the site principal investigator or sub-investigator.
- Recorded on the appropriate SAE form and eCRF.
- Followed through resolution by a licensed study physician listed on the Form FDA 1572 as the site principal investigator or sub-investigator.
- Reviewed and evaluated by an Independent Safety Monitor (ISM) (as deemed necessary), the DSMB (periodic review unless related), DMID, and the IRB.

9.2.5 Procedures to be Followed in the Event of Abnormal Laboratory Test Values or Abnormal Clinical Findings

The site principal investigator or appropriate sub-investigator is responsible for recording all AE/SAEs that are observed or reported during this trial, regardless of the relationship to study product. AE/SAEs, abnormal laboratory test values, or abnormal clinical findings will be collected, assessed, documented, reported, and followed appropriately, using a local laboratory as necessary. In determining eligibility, refer to [section 5.1](#) and the protocol-specific MOP.

9.3 Reporting Procedures

Solicited injection site and systemic reactogenicity events will be documented and reported from the time of each study vaccination through 7 days after each study vaccination.

Clinical safety laboratory AEs will be documented and reported from the time of each study vaccination through approximately 7 days after each study vaccination.

Unsolicited non-serious AEs will be documented and reported from the time of each study vaccination through approximately 21 days after each study vaccination.

SAEs and MAAEs, including NOCMCs and PIMMCs, will be documented and reported from the time of the first study vaccination through approximately 12 months after the last study vaccination.

9.3.1 Serious Adverse Events

Any AE that meets a protocol-defined serious criterion must be submitted immediately (within 24 hours of site awareness) on an SAE form to the DMID Pharmacovigilance Group at the following address:

**DMID Pharmacovigilance Group
Clinical Research Operations and Management Support (CROMS)
[name] [name] 650
[name]**
SAE Hot Line: [name] (US) or [name] (outside US)
SAE [contact] (US) or [name] (outside US)
SAE Email Address: [contact]

In addition to the SAE form, selected SAE data fields must also be entered into AdvantageEDCSM. Please see the protocol-specific MOP for details regarding this procedure.

Other supporting documentation of the event may be requested by the DMID Pharmacovigilance Group and should be provided as soon as possible.

The site will send a copy of the SAE report(s) to the ISM (as deemed necessary) when they are provided to the DMID Pharmacovigilance Group. The DMID Medical Monitor and DMID Clinical Project Manager will be notified of the SAE by the DMID Pharmacovigilance Group. The DMID Medical Monitor will review and assess the SAE for regulatory reporting and potential impact on study subject safety and protocol conduct.

At any time after completion of this trial, if the site principal investigator or appropriate sub-investigator becomes aware of an SAE that is suspected to be related to study product, the site principal investigator or appropriate sub-investigator will report the event to the DMID Pharmacovigilance Group.

9.3.2 Regulatory Reporting for Studies Conducted Under DMID-Sponsored IND

Following notification from the site principal investigator or appropriate sub-investigator, DMID, the Investigational New Drug Application (IND) sponsor, will report any suspected adverse reaction that is both serious and unexpected. DMID will report an AE as a suspected adverse reaction only if there is evidence to suggest a causal relationship between the drug and the AE. DMID will notify FDA and all participating site principal investigators (i.e., all principal investigators to whom the sponsor is providing drug under its IND(s) or under any principal investigator's IND(s)) in an IND safety report of potential serious risks from clinical trials or any other source, as soon as possible, but in no case later than 15 calendar days after the sponsor determines that the information qualifies for reporting as specified in 21 CFR Part 312.32. DMID will also notify FDA of any unexpected fatal or life-threatening suspected adverse reaction as soon as possible, but in no case later than 7 calendar days after the sponsor's initial receipt of the information. Relevant follow-up information to an IND safety report will be submitted as soon as the information is available. Upon request from FDA, DMID will submit to FDA any additional data or information that the agency deems necessary, as soon as possible, but in no case later than 15 calendar days after receiving the request.

All serious events designated as “not related” to study product(s), will be reported to the FDA at least annually in a summary format.

9.3.3 Reporting of Pregnancy

Pregnancies occurring in study subjects will be reported via AdvantageEDCSM on the Pregnancy Report form. No further study vaccinations will be administered to pregnant subjects, but with the subject's permission all protocol-required venous blood samples will be obtained and the subject will continue to be followed for safety for the duration of this trial. Efforts will be made to follow all pregnancies reported during the course of this trial to pregnancy outcome pending the subject's permission.

9.4 Type and Duration of Follow-up of Subjects after Adverse Events

AEs will be collected, assessed, and followed through resolution from the time of each study vaccination through approximately 21 days after each study vaccination.

SAEs and MAAEs, including NOCMCs and PIMMCs, will be collected, assessed, and followed from the time of the first study vaccination through resolution even if this extends beyond the trial-reporting period (approximately 12 months after the last study vaccination).

Resolution of an AE/SAE is defined as the return to pretreatment status or stabilization of the condition with the expectation that it will remain chronic.

Follow-up procedures, evaluations, and outcomes will be recorded on the appropriate DCF.

9.5 Halting Rules

For the purpose of halting rules only events that occur following the administration of the **AS03 adjuvanted 2017 H7N9** will be considered. Further enrollment and study vaccinations will be halted for DSMB review/recommendation if any of the following are reported:

- Any subject experiences ulceration, abscess, or necrosis at the injection site related to study product administration.
- Any 2 or more subjects experience laryngospasm, bronchospasm, or anaphylaxis within 1 day after administration of study product that is considered related to study product.
- Three or more subjects experience generalized urticaria (defined as occurring at more than two body parts) within 3 days after administration of study product that is considered related to study product.
- Any subject experiences an SAE from the time of the first 2017 H7N9 vaccination through 14 days after each 2017 H7N9 vaccination.
- Any subject experiences acute weakness of limbs and/or cranial nerve innervated muscles (description of potential signal of GBS) after administration of study product.
- Any subject develops a PIMMC after administration of study product through the subject's last study visit.

This trial will also be halted for DSMB review/recommendation if, within 7 days after administration of any study vaccination, any of the following occurs within the 2017 A/H7N9 IIV AS03-adjuvanted treatment arms (Group 1 or Group 2).

- 7% or more of subjects (with a minimum of 3 subjects) who received at least one dose of study vaccine to date, cumulative to all 2017 H7N9 vaccine administrations, across Groups 1 and 2, experience the same severe (Grade 3) study vaccine-related injection site reaction. Ecchymosis, erythema, and induration (hardness)/edema (swelling) will also be measured in mm but size will not be used as halting criteria.

- 7% or more of subjects (with a minimum of 3 subjects) who received at least one dose of study vaccine to date, cumulative to all 2017 H7N9 vaccine administration, across Groups 1 and 2, experience the same severe (Grade 3) study vaccine-related subjective systemic reaction, for which the severity (grade) is corroborated by study personnel.
- 7% or more of subjects (with a minimum of 3 subjects) who received at least one dose of study vaccine to date, cumulative to all 2017 H7N9 vaccine administration, across Groups 1 and 2, experience the same severe (Grade 3) study vaccine-related quantitative systemic reaction.
- 7% or more of subjects (with a minimum of 3 subjects) who received at least one dose of study vaccine to date, cumulative to all 2017 H7N9 vaccine administration, across Groups 1 and 2, experience the same severe (Grade 3) study vaccine-related clinical safety laboratory AE.

Grading scales for solicited injection site and systemic (subjective and quantitative) reactions are included in [Section 9.2.2](#).

Grading scales for clinical safety laboratory AEs are included in [Section 9.2.3](#).

If any of the halting rules are met following any subject receipt of any study vaccination, then this trial will not continue with the remaining enrollments or study vaccinations without a review by and recommendation from the DSMB to proceed.

DMID retains the authority to suspend additional enrollment and study interventions/administration of study product during the entire trial, as applicable.

The DMID Medical Monitor is empowered to stop enrollment and study vaccinations if AEs that meet the halting criteria are reported.

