- Subjects will then receive a single dose of study vaccine (Group 1 will receive 2 vaccines) via IM injection into the deltoid muscle of the preferred arm, or if randomized to Group 1, in both arms within 15 minutes of each other. The site of injection (right and/or left arm) and time of administration will be recorded on the appropriate DCF. Subjects will be observed in the clinic for at least 20 minutes after the vaccination. The vaccination site will be examined, post-administration reactogenicity assessments will be performed, and any AE/SAEs will be recorded on the appropriate DCF prior to discharge from the clinic.

- Subjects will be provided with a memory aid and other study-related materials to record daily oral temperature, solicited injection site and systemic reactions, any unsolicited AEs, and concomitant medications. Subjects will be encouraged to take their oral temperature around the same time each day. Subjects must not eat or drink anything hot or cold, or smoke within 10 minutes prior to taking oral temperature. Subjects will be instructed on how to use their memory aid and how to measure and record AEs prior to discharge from the clinic. Subjects will be instructed to notify the study center if they develop any severe reactions after the vaccination(s). If the site principal investigator or appropriate sub-investigator deems the reaction severe enough, further instructions will be given to the subject on the proper course of action, including a return to the clinic for immediate evaluation if appropriate.

8.2 Follow-up Visits, Group 1

Follow-up visits are scheduled in reference to vaccination dates as indicated for each visit window.

8.2.1 Visit 02, Day 4, Memory Aid Review, Phone Call (Window: 3 (± 1) days post Dose 1)

Study personnel will contact subjects by phone to solicit any AE/SAE and concomitant medication information (including solicitation for receipt of any non-study influenza vaccines, including those that are experimental, what type (inactivated or live attenuated), what subtype (e.g., A/H3, A/H5, A/H9) and approximate date of vaccination will be recorded on the appropriate DCF, if known and not previously collected) and review information on their memory aid. Based on the information, subjects may be asked to return to the clinic for evaluation.

8.2.2 Visit 03, Day 8, Clinic Visit (Window: 7 (+2) days post first Dose 1))

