- Subjects will then receive a single dose of study vaccine via IM injection into the deltoid muscle of the preferred arm. If the subject has no preference, the second dose of adjuvanted 2017 H7N9 IIV may be given in either arm as long as there is no hindrance of the reactogenicity assessment. The site of injection (right or left arm) and time of administration will be recorded on the appropriate DCF. Subjects will be observed in the clinic for at least 20 minutes after the vaccination. The vaccination site will be examined, post-administration reactogenicity assessments will be performed, and any AE/SAEs will be recorded on the appropriate DCF prior to discharge from the clinic.
- Subjects will be provided with a memory aid and other study-related materials to record daily oral temperature, solicited injection site and systemic reactions, any unsolicited AEs, and concomitant medications. Subjects will be encouraged to take their oral temperature around the same time each day. Subjects must not eat or drink anything hot

or cold, or smoke within 10 minutes prior to taking oral temperature. Subjects will be instructed on how to use their memory aid and how to measure and record AEs prior to discharge from the clinic. Subjects will be instructed to notify the study center if they develop any severe reactions after the vaccination. If the site principal investigator or appropriate sub-investigator deems the reaction severe enough, further instructions will be given to the subject on the proper course of action, including a return to the clinic for immediate evaluation if appropriate.

**8.2.4 Visit 05, Day 25, Memory Aid Review, Phone Call
(Window: 3 (± 1) days post Dose 2)**

Study personnel will contact subjects by phone to solicit any AE/SAE and concomitant medication information (including solicitation for receipt of any non-study influenza vaccines, including those that are experimental, what type (inactivated or live attenuated), what subtype (e.g., A/H3, A/H5, A/H9) and approximate date of vaccination will be recorded on the appropriate DCF, if known and not previously collected) and review information on their memory aid. Based on the information, subjects may be asked to return to the clinic for evaluation. Note: For subjects who are discontinued from the receipt of Dose 2, AEs will be limited to SAEs and MAAEs, including NOCMCs and PIMMCs.

**8.2.5 Visit 06, Day 29, Clinic Visit
(Window: 7 (+2) days post Dose 2)**

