- Subjects will then receive a single dose of study vaccine via IM injection into the deltoid muscle of the preferred arm. The third vaccination may be given in either arm as long as there is no interference with the reactogenicity assessment. The site of injection (right or left arm) and time of administration will be recorded on the appropriate DCF. Subjects will be observed in the clinic for at least 20 minutes after the vaccination. The third vaccination site will be examined, post-administration reactogenicity assessments will be performed, and any AE/SAEs will be recorded on the appropriate DCF prior to discharge from the clinic.
- Subjects will be provided with a memory aid and other study-related materials to record daily oral temperature, solicited injection site and systemic reactions, any unsolicited AEs, and concomitant medications. Subjects will be encouraged to take their oral

temperature around the same time each day. Subjects must not eat or drink anything hot or cold, or smoke within 10 minutes prior to taking oral temperature. Subjects will be instructed on how to use their memory aid and how to measure and record AEs prior to discharge from the clinic. Subjects will be instructed to notify the study center if they develop any severe reactions after the vaccination. If the site principal investigator or appropriate sub-investigator deems the reaction severe enough, further instructions will be given to the subject on the proper course of action, including a return to the clinic for immediate evaluation if appropriate.

**8.3.7 Visit 08, Day 46, Memory Aid Review, Phone Call
(Window: 3 (± 1) days post Dose 3)**

Study personnel will contact subjects by phone to solicit any AE/SAE and concomitant medication information (including solicitation for receipt of any non-study influenza vaccines, including those that are experimental, what type (inactivated or live attenuated), what subtype (e.g., A/H3, A/H5, A/H9) and approximate date of vaccination will be recorded on the appropriate DCF, if known and not previously collected) and review information on their memory aid. Based on the information, subjects may be asked to return to the clinic for evaluation. Note: For subjects who are discontinued from the receipt of Dose 3, AEs will be limited to SAEs and MAAEs, including NOCMCs and PIMMCs.

**8.3.8 Visit 09, Day 50, Clinic Visit
(Window: 7 (+2) days post Dose 3)**

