9 ASSESSMENT OF SAFETY

9.1 Specification of Safety Parameters

Safety will be assessed by the frequency and severity of:

1. SAEs occurring from the time of the first study vaccination through approximately 12 months after the last study vaccination.
2. Solicited AEs – reactogenicity events occurring from the time of each study vaccination through 7 days after each study vaccination:
 - a) Injection site reactions including pruritus, ecchymosis, erythema, induration (hardness)/edema (swelling), pain, and tenderness.
 - b) Systemic reactions including fever, feverishness, fatigue, malaise, myalgia, arthralgia, headache, and nausea.
3. Clinical safety laboratory AEs occurring from the time of each study vaccination through approximately 7 days after each study vaccination. Parameters to be evaluated include WBC, Hgb, PLT, ALT, T. Bili, Cr.
4. Unsolicited AEs – non-serious AEs occurring from the time of each study vaccination through approximately 21 days after each study vaccination.
5. MAAEs, including NOCMCs and PIMMCs, occurring from the time of the first study vaccination through approximately 12 months after the last study vaccination.

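### As worded, the 7-day limit in Section 9.5 leaves Grade 3 laboratory results from permitted day 8 or 9 draws out of the laboratory halting rule, although they were probably meant to count

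*Protocol*

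**What the plan says.** Section 9.5 restricts all halting rules to events after the AS03-adjuvanted H7N9 vaccine. It then sets out four rules triggered when 7% or more of recipients in Groups 1 and 2 (minimum 3) have the same event. All four share one lead-in: "This trial will also be halted for DSMB review/recommendation if, within 7 days after administration of any study vaccination". Three concern solicited reactions. The fourth is met when enough subjects "experience the same severe (Grade 3) study vaccine-related clinical safety laboratory AE".

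Elsewhere the protocol gives reactions and laboratory events different periods. Section 9.3 says solicited "reactogenicity events will be documented and reported from the time of each study vaccination through 7 days after each study vaccination", but "Clinical safety laboratory AEs will be documented and reported from the time of each study vaccination through approximately 7 days after each study vaccination". Section 9.1 repeats the looser limit: "Clinical safety laboratory AEs occurring from the time of each study vaccination through approximately 7 days after each study vaccination". The primary safety outcome in Section 3.2.1 does the same.

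The post-dose safety bloods are taken at four H7N9-related visits:

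- Group 1, first H7N9 dose, Visit 03 (Section 8.2.2): "Window: 7 (+2) days post first Dose 1"
- Group 1, second H7N9 dose, Visit 06 (Section 8.2.5): "Window: 7 (+2) days post Dose 2"
- Group 2, first H7N9 dose, Visit 06 (Section 8.3.5): the same wording as Group 1 Visit 06
- Group 2, second H7N9 dose, Visit 09 (Section 8.3.8): "Window: 7 (+2) days post Dose 3"

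SAP Section 6.6.1 refers back to Protocol Section 9.5 for the halting rules and does not restate the window.

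**The concern.** A 7-day limit suits reactions, which the subject records daily on a memory aid through 7 days; a clinic visit on day 9 loses none of that information. A laboratory value exists only when blood is drawn, and the scheduled draw cannot fall before day 7. The limit in Section 9.5 therefore meets the first permitted draw day and none of the later ones.

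If the words are followed, whether the laboratory rule is met depends partly on which permitted day subjects happen to return. Two people applying the rule in good faith could disagree on whether a Grade 3 value from a compliant draw counts. A halting rule should not leave that open.

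**Working it through.** The plan states no operating characteristics for the halting rules, so there is no figure to reproduce. The main check is a comparison of windows.

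**Step 1. Permitted draw days.** Vaccination day is Day 1, so Day 8 [+2] in the schedule means 7 to 9 days after the dose. The window has no early side. Permitted days: 7, 8, 9. Within the literal limit: 7. Outside it: 8 and 9. This holds at all four visits listed above. (Group 2 Visit 03 is printed as 7 (±2), but it follows IIV4 alone and is outside these rules.)

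**Step 2. Numerator and denominator.** The denominator is recipients to date. A subject drawn on day 8 or 9 remains in it; only the result is left out. The number of subjects needed is t(n) = max(3, ceil(0.07n)): 3 for n up to 42, 4 for n = 43 to 57, 9 for n = 115 to 120 (0.07 × 120 = 8.4).

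**Step 3. What an illustration needs.** Let f be the share of draws made exactly 7 days post dose and p the true rate of the same related Grade 3 event. Neither is in the documents, so both are assumptions. I also take draw day as independent of the result, and results as known at once.

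*One draw per subject.* The per-subject chance of a counted event is pf, so the literal rule acts like a threshold of 7%/f on all results: 8.75% at f = 0.8, 14% at f = 0.5, 21% at f = 1/3. If exactly 3 events arise among 42 or fewer recipients, all 3 count with probability f³ = 0.512, 0.125, 0.037.

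*Two draws per subject.* Each subject has two H7N9 doses and the rule is cumulative over them. If the event is present at both draws, at least one counts with probability 1 − (1 − f)² = 0.96, 0.75, 0.556.

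The chance of ever reaching t(n), checked after each of 120 recipients (exact recursion) with p = 0.07, is:

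| f | one draw | two draws, event at both |
|---|---|---|
| 1 | 0.765 | 0.765 |
| 0.8 | 0.579 | 0.733 |
| 0.5 | 0.239 | 0.524 |
| 1/3 | 0.091 | 0.299 |

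With a single look at n = 120 and one draw, P(X ≥ 9) is 0.465, 0.231, 0.026 and 0.002 for the same values of f.

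The spread between columns and between looks shows how far the answer depends on assumptions the documents do not supply.

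**The case against.** The strongest reply is that the protocol treats this visit as its 7-day assessment. Sections 4 and 7.2.1 say laboratory samples are taken approximately 7 days after each vaccination, Section 7.1 describes the Day 8 visit as the 7-day review, and Section 9.6.2 speaks of 8-day laboratory data. The laboratory bullet also uses the same term, clinical safety laboratory AE, that is defined elsewhere with the looser limit. This stands as evidence of intent, though the 8-day label is weak support: with vaccination on Day 1, Day 8 is 7 days post dose.

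Section 8.5 applies a within-7-days condition to an early-termination laboratory draw, which could suggest a strict meaning. But the same list uses within 21 days for antibody blood, where the scheduled visits are 21 (+7) days. It settles nothing either way.

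It can also be said that Section 9.5 asks when an event occurs, not when blood is drawn, and a value found on day 8 may have arisen by day 7. That does not remove the problem, because a laboratory AE is normally dated by its draw.

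Other safeguards exist. Under Section 5.2.3 a Grade 3 value that does not fall to Grade 2 or less blocks that subject's next dose. DMID may suspend at any time, and the DSMB may meet ad hoc. These limit harm but act on one subject or at discretion. The 25% and 75% DSMB reviews are keyed to the first study vaccination, which in Group 2 is IIV4 alone. The DSMB charter or report shell may already settle the point; neither is among these documents.

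Two stronger inferences are tempting. A reader might conclude that day 8 and 9 results will be ignored in practice. The documents do not show that, and the surrounding text points the other way. A reader might also take the trigger probabilities above as the size of the loss. They are not: f and p are assumed, and allowing for the second draw alone can move 0.239 to 0.524.

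**Conclusion.** The mismatch is real and follows directly from the text: one 7-day limit governs a laboratory rule whose scheduled draw is permitted on days 7, 8 and 9. Read as written, related Grade 3 results from the last two of those days do not count, and their subjects stay in the denominator. The likely intent is that they do count.

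The loss is zero on that reading, or if every draw falls on day 7. Otherwise it cannot be quantified from the documents. I rate this as minor: a wording defect in a stated safety rule, worth correcting because the rule should give every user the same answer. My confidence is medium, since the charter or report shell could already resolve it.

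**What to change.** In the laboratory bullet of Section 9.5, state that Grade 3 results obtained after each H7N9 dose through the Day 8 (+2) safety visit, that is through 9 days post dose and including any earlier unscheduled draw, count toward the 7% rule. The visits are Group 1 Visits 03 and 06 and Group 2 Visits 06 and 09. Ending at 9 days matches the existing window and does not bring in out-of-window draws. Leave the threshold, the grades and the three reaction bullets unchanged.

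The cost is a short protocol amendment, submitted to the IRBs for up to 4 sites. If the inclusive reading was always meant, nothing changes operationally. Compared with the literal reading, a halt for DSMB review becomes more likely when the true rate is low. As an illustration with one draw per subject and a check after each of 120 recipients, going from f = 0.5 to counting all draws moves the chance of ever triggering from 0.001 to 0.009 at a true rate of 1%, from 0.009 to 0.062 at 2%, and from 0.029 to 0.168 at 3%. Such a halt leads to a review and does not by itself end the trial.
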